5.3.5.9 Preexisting Medical Conditions

A preexisting medical condition is one that is present at the screening visit for this study. Such conditions should be recorded on the General Medical History and Baseline Conditions eCRF.

A preexisting medical condition should be recorded as an adverse event only if the frequency, severity, or character of the condition worsens during the study. When recording such events on the Adverse Event eCRF, it is important to convey the concept that the preexisting condition has changed by including applicable descriptors (e.g., "more frequent headaches").

5.3.5.10 Lack of Efficacy or Worsening of Incurable, Advanced Malignancy

Events that are clearly consistent with the expected pattern of progression of the underlying disease should not be recorded as adverse events. These data will be captured as efficacy assessment data only. In most cases, the expected pattern of progression will be based on RECIST criteria. In rare cases, the determination of clinical progression will be based on symptomatic deterioration. However, every effort should be made to document progression through use of objective criteria. If there is any uncertainty as to whether an event is due to disease progression, it should be reported as an adverse event.

5.3.5.11 Hospitalization or Prolonged Hospitalization

Any adverse event that results in hospitalization (i.e., inpatient admission to a hospital) or prolonged hospitalization should be documented and reported as a serious adverse event (per the definition of serious adverse event in Section 5.2.2), except as outlined below.

An event that leads to hospitalization under the following circumstances should not be reported as an adverse event or a serious adverse event:

- Hospitalization for respite care
- Hospitalization solely for coordination of care, including hospice arrangements
- Planned hospitalization required by the protocol (e.g., for study drug administration, protocol mandated observation window, insertion of access device for study drug administration, etc.)
- Hospitalization for a preexisting condition, provided that all of the following criteria are met:

The hospitalization was planned prior to the study or was scheduled during the study when elective surgery became necessary because of the expected normal progression of the disease.

The patient has not experienced an adverse event.

- Hospitalization due solely to progression of the underlying cancer
- Hospitalization that was necessary because of patient requirement for outpatient care outside of normal outpatient clinic operating hours

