4.3.2.2 Pembrolizumab

Pembrolizumab will be administered at a dose of 200 mg as an IV infusion over 30 (± 10) minutes.

If pembrolizumab is administered in combination with RO7198457 (safety run-in stage and Arm B), refer to [REDACTED] for prophylactic treatment and RO7198457 administration information.

Vital signs (pulse rate, respiratory rate, blood pressure and temperature) should be recorded within 60 minutes prior to the infusion. If clinically indicated, vital signs should be recorded during the infusion at 15, 30, 45, and 60 minutes (± 5 minutes for all timepoints) during the infusion and at 30 (± 10) minutes after the infusion. If the patient experienced an IRR with the previous infusion or if clinically indicated, vital signs should be recorded during the infusion and at 30 (± 5) minutes after the infusion.

Patients should be observed for 30 minutes after the infusion. Patients may be hospitalized overnight if required by institutional guidelines. If infusion-related adverse events (e.g., fever, chills) are not resolved to \leq Grade 1 following the outpatient observation period, patients should be admitted for overnight observation.

Patients should be informed about the possibility of delayed post-infusion symptoms and instructed to contact their study physician if they develop such symptoms.

Guidelines for dosage modification and treatment interruption or discontinuation are provided in Section 5.1.4. Guidance on study drug administration in the context of management of specific adverse events is provided in Section 5.1.4.3.

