5.2.2 Serious Adverse Events (Immediately Reportable to the Sponsor)

A serious adverse event is any adverse event that meets any of the following criteria:

- Is fatal (i.e., the adverse event actually causes or leads to death)
- Is life threatening (i.e., the adverse event, in the view of the investigator, places the patient at immediate risk of death)

This does not include any adverse event that, had it occurred in a more severe form or was allowed to continue, might have caused death.

- Requires or prolongs inpatient hospitalization (see Section [5.3.5.11](#))
- Results in persistent or significant disability/incapacity (i.e., the adverse event results in substantial disruption of the patient's ability to conduct normal life functions)
- Is a congenital anomaly/birth defect in a neonate/infant born to a mother exposed to study drug
- Is a significant medical event in the investigator's judgment (e.g., may jeopardize the patient or may require medical/surgical intervention to prevent one of the outcomes listed above)

The terms "severe" and "serious" are not synonymous. Severity refers to the intensity of an adverse event (e.g., rated as mild, moderate, or severe, or according to NCI CTCAE;

see Section 5.3.3); the event itself may be of relatively minor medical significance (such as severe headache without any further findings).

Severity and seriousness need to be independently assessed for each adverse event recorded on the eCRF.

Serious adverse events are required to be reported by the investigator to the Sponsor immediately (i.e., no more than 24 hours after learning of the event; see Section 5.4.2 for reporting instructions).

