5.3.5.1 Systemic Infusion Reactions During or After Study Drug Infusion

Adverse events that occur during or within 24 hours after completion of study drug administration and are judged to be related to study drug infusion(s) should be captured as a diagnosis (e.g., "flu-like symptoms," "infusion-related reaction," "cytokine release syndrome" or other adverse event term denoting the overall diagnosis) on the Adverse Event eCRF based on the most clinically-significant individual adverse event, its timing, and any required interventions.

For example, mild to moderate presentation that may include fever, chills or other constitutional symptoms, may be best described as flu-like symptoms, whereas more severe events, such as hypotension, hypoxia or signs of organ toxicity, may be signs of CRS. Events that occur during or shortly after the infusion may be referred to as "infusion-related reaction." Clinical symptoms that include dyspnea, bronchospasm, chest tightness, urticaria, angioedema, hypotension and other cardiovascular symptoms, and (pre-)syncope may be indicative of hypersensitivity, allergic reaction or anaphylaxis.

If possible, avoid ambiguous terms such as "systemic reaction." Associated signs and symptoms should be recorded on the dedicated Infusion-Related Reaction eCRF. If a patient experiences both a local and systemic reaction to the same dose of study drug, each reaction should be recorded separately on the Adverse Event eCRF, with signs and symptoms also recorded separately on the dedicated Infusion-Related Reaction eCRF. [REDACTED]

[REDACTED]

[REDACTED]

[REDACTED] Section 5.2.3 for details on adverse events of special interest, and Section 5.3 for reporting requirements.

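### Section 5.3.5.11 exempts the adverse event, not only the hospital stay, from reporting, and leaves the seriousness of an admission for an infusion reaction unsettled

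*Combined protocol and SAP*

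**What the plan says.** Section 5.3.5.11 starts from a general rule: an adverse event leading to hospital admission "or prolonged hospitalization should be documented and reported as a serious adverse event", subject to exceptions. The exceptions are introduced with "An event that leads to hospitalization under the following circumstances should not be reported as an adverse event or a serious adverse event". Six circumstances follow, and three matter here.

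- **Protocol-required stays:** "Planned hospitalization required by the protocol (e.g., for study drug administration, protocol mandated observation window", with insertion of an access device as a further example.
- **Preexisting condition:** exempt only if every listed condition is met, one of which is that no adverse event has occurred.
- **Out-of-hours stays:** the patient needed care of an outpatient kind while the clinic was closed. This bullet does not require the stay to be planned and does not exclude patients who have had an adverse event.

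Four other sections bear on the same patients.

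- **Section 5.2.2** makes an event serious if it "Requires or prolongs inpatient hospitalization".
- **Section 5.3.1** requires all adverse events after the start of study drug to be reported, until 90 days after the final dose or the start of another anti-cancer therapy.
- **Section 5.3.5.1** says that related events during or within 24 hours after dosing "should be captured as a diagnosis" on the Adverse Event eCRF, with signs and symptoms on a dedicated form.
- **Section 4.3.2.2** (pembrolizumab) deals with infusion-related events such as fever or chills that are still above Grade 1: "following the outpatient observation period, patients should be admitted for overnight observation". It also allows stays with no reaction at all: "Patients may be hospitalized overnight if required by institutional guidelines".

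**The concern.** An exemption for routine stays is normal: a night in hospital for convenience should not turn a non-event into a serious adverse event. For that purpose it is enough to say that the stay does not count as a seriousness criterion. Section 5.3.5.11 goes further and removes the event itself from adverse event reporting.

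Two things follow. First, a site that applies the out-of-hours bullet as written would leave a real adverse event off the form that Sections 5.3.1 and 5.3.5.1 require. Second, a site that admits a patient under Section 4.3.2.2 has no clear instruction on whether that admission makes the reaction serious. Serious status decides whether the event goes to the sponsor within 24 hours (Section 5.4). It also affects how the event appears in the data that the Internal Monitoring Committee sees (Section 3.1.5) and whether it enters the serious adverse event summary by arm (Section 6.5).

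**Working it through.** The plan gives no figure on this point and no arithmetic applies. The check sets the passages side by side.

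1. **What the exemption acts on.** The general rule in Section 5.3.5.11 concerns adverse events that lead to admission, and the list is a carve-out from that rule. So the list can apply to patients with a real adverse event, and its lead-in removes both the adverse event report and the serious adverse event report.

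2. **Out-of-hours bullet.** Take a patient on study drug who develops an adverse event in the evening and is kept overnight only because the clinic is closed.
   - Section 5.3.5.11, read literally: report neither.
   - Section 5.3.1: report the adverse event.
   - Section 5.3.5.1, if the event is related and within 24 hours of dosing: record it as a diagnosis on the Adverse Event eCRF.

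   These instructions are opposite, and no readable text says which prevails. The preexisting-condition bullet avoids the conflict by requiring that no adverse event has occurred; the out-of-hours bullet has no such guard.

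3. **Protocol-required bullet.** Take a patient with a Grade 2 fever that persists after the observation period and who is admitted under Section 4.3.2.2.
   - *Reading A:* the admission responds to an event that has already happened, so it is not planned and the exemption does not apply. The reaction is an adverse event and, if the stay is an inpatient admission, a serious one under Section 5.2.2 and the general rule of Section 5.3.5.11.
   - *Reading B:* the protocol directs the stay, so it counts as a mandated observation window. Then Section 5.3.5.11 removes both reports, against Sections 5.3.1 and 5.3.5.1.

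   Reading A is the more natural, because the bullet is limited to planned stays and its examples are all fixed in advance. Section 5.3.5.11 does not say so.

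4. **Other routes to a report.** Section 5.2.3 makes Grade 3 or higher hypoxia, dyspnea or hypotension within 24 hours immediately reportable, and the severity table in Section 5.3.3 makes Grade 4 and 5 events serious. Neither reaches the Grade 2 fever in step 3. In the readable text, its 24-hour report depends on the hospitalization criterion or on the investigator judging the event medically significant.

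5. **A model in the same document.** Section 5.3.5.12 keeps the circumstance (overdose or medication error) apart from any adverse event that results and has each recorded. Section 5.3.5.11 does not make that separation.

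**The case against.** The strongest reply is that the protocol, read as a whole, already gives the right answer. The protocol-required bullet is limited to planned stays, which an admission for an unresolved reaction is not. The out-of-hours bullet concerns outpatient care, which is not what a patient needs if Section 4.3.2.2 directs admission; closing time is not the trigger there. Section 5.3.5.1 is the specific rule for infusion reactions, and its readable text makes no exception for admitted patients. Section 5.3.1 covers everything else.

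Most of this stands for Section 4.3.2.2 admissions. A reader might infer that the persistent infusion reactions drop out of the safety data. The documents do not support that: a reaction is lost altogether only if a site puts Section 5.3.5.11 above both Section 5.3.1 and Section 5.3.5.1. What the reply leaves open is the literal instruction in the out-of-hours bullet, which conflicts with Section 5.3.1 for any adverse event, and the unstated seriousness of the Section 4.3.2.2 admission.

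A reader might also infer that the combination arm is made to look safer. That is not established. The only readable admission trigger is in the pembrolizumab section, which applies to both arms. The RO7198457 administration text, two items in the list of events of special interest and part of Section 5.3.5.1 are redacted and may settle how vaccine reactions are observed and reported.

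**Conclusion.** The point holds as a wording conflict, with moderate confidence. Section 5.3.5.11 exempts events where it needs only to exempt stays. For out-of-hours care, its literal instruction contradicts Sections 5.3.1 and 5.3.5.1. For admissions under Section 4.3.2.2, the likely consequence is inconsistent assignment of seriousness between sites, not loss of the adverse event record.

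The size cannot be put in numbers. It is tempting to count the 11 RO7198457 days implied by the cytokine row of Appendix 3 with its footnote g, multiply by the 80 planned Arm B patients (11 x 80 = 880) and apply an assumed admission rate. That would not be evidence. The 880 assumes that every patient is dosed through Cycle 29, the documents give no admission rate, and the result would apply a pembrolizumab trigger to vaccine days and treat every admitted reaction as misreported.

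The conclusion rests on the readable text. If the redacted sections define the observation window or the reporting of admitted reactions, the second part of the point could narrow. The conflict in the out-of-hours bullet would remain unless they also state which rule prevails.

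**What to change.** Three wording changes; the admission rule in Section 4.3.2.2 is a clinical matter and is not questioned here.

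1. Reword the lead-in of Section 5.3.5.11 so that the listed circumstances only stop the hospitalization itself from making an event serious, and any adverse event is still recorded on the Adverse Event eCRF under Sections 5.3.1 and 5.3.5.1. Expected disease progression stays governed by Section 5.3.5.10.
2. If the sponsor wants nothing reported under a given bullet, attach the no-adverse-event condition already used in the preexisting-condition bullet. The out-of-hours and protocol-required bullets are the ones that lack it here.
3. Reconcile Sections 4.3.2.2, 5.2.2, 5.3.5.1 and 5.3.5.11 by stating how an admission triggered by an unresolved infusion-related event is classified for seriousness, as distinct from a routine institutional overnight stay with no event.

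The cost is a short amendment centered on Section 5.3.5.11 and a memo to sites. The downside is somewhat more adverse event and serious adverse event reports.

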5.3.5.12 Cases of Accidental Overdose or Medication Error

Accidental overdose and medication error (hereafter collectively referred to as "special situations"), are defined as follows:

- Accidental overdose: accidental administration of a drug in a quantity that is higher than the assigned dose
- Medication error: accidental deviation in the administration of a drug

In some cases, a medication error may be intercepted prior to administration of the drug.

Special situations are not in themselves adverse events, but may result in adverse events. Each adverse event associated with a special situation should be recorded separately on the Adverse Event eCRF. If the associated adverse event fulfills seriousness criteria *or qualifies as an adverse event of special interest*, the event should be reported to the Sponsor immediately (i.e., no more than 24 hours after learning of the event; see Section 5.4.2). For RO7198457, adverse events associated with special situations should be recorded as described below for each situation:

- Accidental overdose: Enter the adverse event term. Check the "Accidental overdose" and "Medication error" boxes.
- Medication error that does not qualify as an overdose: Enter the adverse event term. Check the "Medication error" box.
- Medication error that qualifies as an overdose: Enter the adverse event term. Check the "Accidental overdose" and "Medication error" boxes.

In addition, all special situations associated with RO7198457, regardless of whether they result in an adverse event, should be recorded on the Adverse Event eCRF. Special situations should be recorded as described below:

- Accidental overdose: Enter the drug name and "accidental overdose" as the event term. Check the "Accidental overdose" and "Medication error" boxes.
- Medication error that does not qualify as an overdose: Enter the name of the drug administered and a description of the error (e.g., wrong dose administered, wrong dosing schedule, incorrect route of administration, wrong drug, expired drug administered) as the event term. Check the "Medication error" box.
- Medication error that qualifies as an overdose: Enter the drug name and "accidental overdose" as the event term. Check the "Accidental overdose" and "Medication error" boxes. Enter a description of the error in the additional case details.
- Intercepted medication error: Enter the drug name and "intercepted medication error" as the event term. Check the "Medication error" box. Enter a description of the error in the additional case details.

As an example, an accidental overdose that resulted in a headache would require two entries on the Adverse Event eCRF, one entry to report the accidental overdose and one entry to report the headache. The "Accidental overdose" and "Medication error" boxes would need to be checked for both entries.

5.3.5.13 Patient-Reported Outcome Data

Adverse event reports will not be derived from PRO data (e.g., EORTC QLQ-C30, PRO-CTCAE, and WPAI) by the Sponsor, and safety analyses will not be performed using PRO data. Sites are not expected to review the PRO data for adverse events.

5.4 IMMEDIATE REPORTING REQUIREMENTS FROM INVESTIGATOR TO SPONSOR

Certain events require immediate reporting to allow the Sponsor to take appropriate measures to address potential new risks in a clinical trial. The investigator must report such events to the Sponsor immediately; under no circumstances should reporting take place more than 24 hours after the investigator learns of the event. The following is a list of events that the investigator must report to the Sponsor within 24 hours after learning of the event, regardless of relationship to study drug:

- Serious adverse events (defined in Section 5.2.2; see Section 5.4.2 for details on reporting requirements)
- Adverse events of special interest (defined in Section 5.2.3; see Section 5.4.2 for details on reporting requirements)
- Pregnancies (see Section 5.4.3 for details on reporting requirements)

The investigator must report new significant follow-up information for these events to the Sponsor immediately (i.e., no more than 24 hours after becoming aware of the information). New significant information includes the following:

- New signs or symptoms or a change in the diagnosis
- Significant new diagnostic test results
- Change in causality based on new information
- Change in the event's outcome, including recovery
- Additional narrative information on the clinical course of the event

Investigators must also comply with local requirements for reporting serious adverse events to the local health authority and IRB/EC.

5.4.1 Emergency Medical Contacts

To ensure the safety of study participants, access to the Medical Monitors is available 24 hours per day, 7 days per week. Details will be provided separately.

5.4.2 Reporting Requirements for Serious Adverse Events and Adverse Events of Special Interest

5.4.2.1 Events That Occur prior to Study Drug Initiation

Once the electronic data capture (EDC) system is available, all information will need to be entered and submitted via the EDC system

After informed consent has been obtained but prior to initiation of study drug, only serious adverse events caused by a protocol-mandated intervention should be reported. In the event the EDC system is unavailable, the paper Clinical Trial Serious Adverse Event/Adverse Event of Special Interest Reporting Form provided to investigators should be completed and submitted to the Sponsor or its designee immediately (i.e., no more than 24 hours after learning of the event), either by faxing or by scanning and emailing

the form using the fax number or email address provided to investigators by emailing the form using the following email address: [contact]

5.4.2.2 Events That Occur after Study Drug Initiation

After initiation of study drug, serious adverse events and adverse events of special interest will be reported until 90 days after the final dose of study drug or until initiation of subsequent systemic anti-cancer therapy, whichever occurs first. Investigators should record all case details that can be gathered immediately (i.e., within 24 hours after learning of the event) on the Adverse Event eCRF and submit the report via the EDC system. A report will be generated and sent to Safety Risk Management by the EDC system.

In the event that the EDC system is unavailable, the paper Clinical Trial Serious Adverse Event/Adverse Event of Special Interest Reporting Form provided to investigators should be completed and submitted to the Sponsor or its designee immediately (i.e., no more than 24 hours after learning of the event), either by faxing or by scanning and emailing the form using the fax number or email address provided to investigators. Once the EDC system is available, all information will need to be entered and submitted via the EDC system.

Instructions for reporting serious adverse events that occur >90 days after the final dose of study treatment are provided in Section [5.6](#).

